3.5. Participant Timeline

Table 2: Participant Timeline

3.6. Sample size

We will enroll 10 participants in the gabapentin trial. In personalized trials, sample size refers to the number of assessments for each patient. As we had no prior data from which to estimate within patient day-to-day variability in pain scores nor an expected effect size for symptom reduction when comparing gabapentin to placebo in this population, we did not calculate statistical power a priori for the number of assessments per treatment period. Rather, the sample size for each personalized trial was based on collecting the maximal amount of data expected to be tolerable from the perspective of patient study burden. Ten participants is a sampling number based on current recruitment into the PIUO Study (REB #H16-03288) from which we expect to draw the majority of participants for this trial. This number, with the repeated measures obtained throughout the treatment periods should provide sufficient data to address the study goals.

3.7. Recruitment

Participants may be recruited from within the province of British Columbia exclusively. Recruitment will be via publicly displayed posters, social media channels, and referral from clinicians in accordance with ethical guidelines from the UBC Research Ethics Board (REB). Targeted recruitment will be made amongst participants in another health services study lead by the Sponsor, "Optimizing the Management of Pain and Irritability in Children with Severe Neurological Impairment" (The PIUO Study) (REB #H16-03288). Those participants in the PIUO Study who continue to experience unexplained pain and irritability despite thorough investigations and who have indicated in writing that they consent to receive information about research initiatives related to this issue, will be invited to take part in the trial.

3.8. Trial Procedures and Evaluations

Screening

Screening will be performed prior to the Baseline Visit as a preliminary assessment of the participant's eligibility. Screening will take place over the phone. The researchers will explain the study to the prospective participant in lay terms, including possible side effects of the therapy. The researchers will use the Eligibility Assessment to confirm whether the prospective participant is eligible. The Eligibility Assessment includes confirmation of the prospective participants':

- Age (must be between 3 and 18 years old)
- GMFCS level (must be 3, 4 or 5)
- CFCS level (must be 4 or 5)
- Pain Score (must be 3 or higher)*
- Pain Identification (must be PIUO, evidenced by a score of 3 or higher)*
- * A Pain Score of 3 refers to the eligibility screening for the PIUO study, which potential participants may have participated in. The eligibility screening for the PIUO study includes a score to identify the pain as PIUO and a score to measure the persistence and distress level of the pain congruent with the Pain Survey scores of C, D, or E. In the eligibility screening these components are numerical scores.

If eligible, the prospective participant will be provided with the Consent Form. Upon receiving the signed Consent Form the researchers will schedule a Baseline Visit. Prior to the Baseline Visit the researchers will collect data from all medical records to fill out the Health Information Form. The data collected will be confirmed with the participant at the Baseline Visit. The participant will also receive the Demographic Information, the NCPCC-R and the POMIS-57 to complete immediately prior to the Baseline Visit.

Some children will already have completed evaluation via the PIUO Pathway, either as part of our current, ongoing study of children with PIUO, or by their primary provider who has used the PIUO

Pathway approach. These children will not need to undergo re-evaluation, but can move directly to the gabapentin trial.

If a subject who otherwise meets inclusion criteria has not undergone the evaluation for treatable, nociceptive-inflammatory causes of pain and irritability described by the PIUO Pathway, then we will conduct a PIUO Pathway evaluation first. If a treatable cause is identified, then the child will be referred back to their primary health care provider, and will not be enrolled in the gabapentin trial. If no treatable cause is found, then the child may continue onto the gabapentin trial. It is expected that undertaking a full PIUO Pathway evaluation may take 2-4 weeks time.

Baseline Visit

The Baseline Visit will be in person and will last approximately 2 hours. The following activities will be conducted prior to drug dispensing:

- Medical history: The participant will be asked to confirm findings in the Health Information Form. The following clinical information will also be collected for each participant:
 - o Any pre-existing medical conditions/signs/symptoms as part of the medical history.
 - o List of concomitant medications, dosage and date of treatment initiation
- Vital signs: Seated blood pressure (BP), heart rate (HR), respiration rate, oxygen saturation (SpO2), temperature, weight and height will be recorded.
- A head to toe physical exam will be performed
- The participant will be asked to complete the following at the Baseline Visit:
 - o Demographic Information (Appendix 3)
 - o Pain Survey (Appendix 5)
 - o NCPCC-R (Appendix 7)
 - o PROMIS-57 (Appendix 8)

In addition to reviewing all previous clinical work-up related to pain and irritability, we will establish a baseline for participants' expectations to the effectiveness of gabapentin. Pain is highly modifiable by psychological factors such as beliefs and expectations, which may influence treatment response (via placebo analgesia). This is especially important in this context of children with SNI where caregivers play a key role in assessment and management of pain and a placebo-by-proxy effect might occur based on the parents' perceptions/behavior. To evaluate the Impact of Expectations all families will be asked at the Baseline Visit if they expect participation in the trial will be of benefit to their child and at Follow Up they will be asked if the trial was of benefit to them and/or their child. They will also be asked after each sequence whether they believe their child received medication or placebo.

Randomization

Randomization will be undertaken by the study pharmacist, using a computer-generated randomization. Before the 2 periods (pair of active drug (G) or placebo (P)) the pharmacist will generate a random code indicating whether G or P is to be given first. The randomization table will be kept in the Research Pharmacy office, which has restricted access. In case of a serious adverse event and when necessary, the randomization of any one participant can be unmasked to the Principal Investigator. This will be done through direct contact between the pharmacist and the Principal Investigator.

Study Contacts

Contact with study participants during the trial will consist of online surveys and telephone check ins. Contacts will be scheduled to overlap with changes in dose. Each contact will last approximately 10 minutes. The following study tools will be used at study contacts (see table 4 for a schedule of assessments at the time of study contacts):

- Health Update (Appendix 6) (midway through each sequence and at study end)
- Pain Survey (Appendix) (only on the first or last day of each block, not both)
- NCCPC-R (Appendix 7)
- PROMIS-57 (Appendix 8)
- Adverse Events Log (Appendix 10)
- Concomitant Medications (Appendix 11)

When the participant begins Sequence 2, the drug will be dispensed again in person.

Follow up

Two weeks past Study End the randomization sequence for individual participants will be unblinded and shared with the participants along with their individual results. The results will be presented numerically and graphically. Graphs showing the outcomes over time on the medication and placebo arms, summarizing the dosage used at individual outcome points will be provided. This will allow participants to make decisions regarding continuing gabapentin (in consultation with their primary caregiver) and is in keeping the Strategies for Patient Oriented Research (SPOR) principles that this clinical care trial is based on. At this time, the participant's caregiver will also be given the opportunity to provide feedback to the research team via the Participation Questionnaire (Appendix 9).

For any participant that experiences a SAE, there will be an initial contact at the time of the event and appropriate evaluation undertaken by the physician investigator. Another safety follow-up visit will be scheduled within 7 days following the final study visit to review the event. Additional follow-up may be done based on the investigator's medical judgment.

Missed visits

If a participant misses a scheduled study visit or contact with prior permission, the researchers will try to contact him/her and schedule a visit as soon as possible. Participants who stop taking the study medication for any reason will be asked to complete the Final Study Visit.

Withdrawal from trial

A participant may be withdrawn from the trial due to the following reasons including, but not limited to:

- Participant's request
- Severe Adverse Events (SAE) and/or other safety reasons
- A new health condition appears that is suspected to require care or medications prohibited by the protocol

• It is in the participant's best interest according to the Investigator's clinical judgment

Participants are free to withdraw from the study at any time and for whatever reason, specified or unspecified, and without prejudice to his or her medical care by a physician.

All premature discontinuations and their causes must be documented by the Investigator on the appropriate CRF pages. The reason for, and date of, the discontinuation, and the date of the last dose of the study medication, must be recorded in the appropriate section of the CRF. While the treatment with the investigational product will discontinue if a participant withdraws from the trial, participants not completing the entire study should be fully evaluated (i.e., last study contact and follow up procedures performed), wherever possible.

Withdrawn participants will be replaced via ongoing recruitment in order to meet the goal of obtaining data from 10 participants completing the trial.

Early termination visit

If a participant withdraws or is removed from the trial for any reason prior to the completion of the trial, the reason for, and date of, the discontinuation, and date of the last dose of study drug, must be recorded in the appropriate section of the Case Report Form (CRF).

At the time of discontinuation, every effort should be made to ensure that: (1) Procedures and evaluations scheduled for the End of Study are performed, including the assessment of AEs. (2) Study drugs are returned and inventoried. (3) Study staff make an appointment for a safety follow-up visit if required.

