Summary: This study uses a rapid and safe dose escalation to the widely accepted therapeutic range where evaluation of response will be undertaken with frequent scoring. Different maximal doses are used for children < or ≥ 15 kg, based on pharmacokinetic data. Doses are titrated to clinical effect or maximum target dose, whichever is lower. Once in the therapeutic range, doses change after 3 days if there is not an adequate reduction in symptoms. For any subject that obtains clinical benefit below maximal dose, then they will be held at that dose for the remainder of that period until such time as the scheduled wean begins. At the end of each treatment period there is a wash-out.

Starting Dose: The starting dose of gabapentin will be 5 mg/kg administered as oral liquid or via gastric or jejunal routes. On Day 1 of the study, the gabapentin will be administered once at bed-time and then increased according to the schedule shown in Table 1.

Dose Escalation: The dose will be increased every 3^{rd} - 4^{th} day in a step wise fashion of 13% - 50%, starting with the evening dose in order to accommodate sedation. The maximum dose for subjects will be as follows: < 15 kg to 60 mg/kg day and \geq 15 kg to 45 mg/kg/day. Dose titration will be to a maximum target dose (based on weight as described, < 15 kg, > 15kg) or to clinical effect, whichever is lower. The dose escalation scheme is based upon expert consensus and personal communication with [name], [name], and upon review with the BC Children's Hospital research pharmacist. \cdot , 56.

Some children with PIUO and SNI have been given gabapentin empirically by their health care provider, often without any subsequent, detailed assessment of benefit. Many times, the medication is continued because of its low side-effect profile and overall safety compared with other analgesics. If a subject is currently on gabapentin at the time of enrolment, and the parent/caregiver wants an evaluation of its effectiveness, then the subject can be enrolled in this study with the following approach:

After appropriate enrolment and consent, the subject will be weaned off of gabapentin, in a stepwise manner with 25% reductions in dose every 3rd day. Once they are no longer on the active drug, they will be randomized to active drug or placebo like all other study participants.

Gabapentin Risks and Precautions

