The risk of serious side effects of respiratory depression with concomitant use with opioids is acknowledged (BC Children's Hospital Integrated Pain Service Gabapentin Information http://www.bcchildrens.ca/Pain-Services-Site/Docu-Sheet. Accessed at: ments/BCCH1455Gabapentin.pdf. Retrieved on October 4, 2020). A minority of patients might be on opioids. Dose adjustments will be added when gabapentin is used with a concomitant opioid or other CNS depressant medication: the family will be advised to return to the previous stable, safe dose in the protocol, and the subject will remain at that dose with no further escalation for the duration of the trial arm. This schedule will be duplicated on the parallel arm (active drug or placebo) to maintain masking. The participants are highly monitored, often with continuous oxygen saturation monitoring and/or "baby-cam" devices observing them during sleep. During the daytime they are with family, or professional caregivers (aides, nurses, etc.). These individuals will be advised to watch for respiratory depression and sedation that occur well before fatal apnea, and how to respond.

While there are no prohibitions on concomitant care, any care or medications unrelated to the trial will be noted in the CRFs for each participant.

Participants are sometimes obtaining respite care at facilities with nursing and physician care. Medical reconciliation is done at each admission. Parents will be provided with a letter to share with these programs outlining the study, the drug being tested, and a 24-hour pager to contact for further information or concerns

Active Participants < 15kg in mg per kg

Day	Morning mg/kg	Noon mg/kg	Evening mg/kg	Total mg/kg per day	% Change
1*	0	0	5	5	0
2	0	5	5	10	100%
3	5	5	5	15	50%
4	5	5	5	15	0%
5	5	5	10	20	33%
6	5	5	10	20	0%
7	5	5	10	20	0%
8	10	10	10	30	50%
9	10	10	10	30	0%
10	10	10	10	30	0%
11	13.3	13.3	13.3	40	33%
12	13.3	13.3	13.3	40	0%
13	13.3	13.3	13.3	40	0%
14	17	17	17	50	25%
15	17	17	17	50	0%
16	17	17	17	50	0%
17	20	20	20	60	20%
18	20	20	20	60	0%
19	20	20	20	60	0%
20	13.3	13.3	13.3	40	-33%
21	6.7	6.7	6.7	20	-50%
22	0	5	5	10	-50%
23	0	0	5	5	-50%
24	0	0	0	0	-100%
25	0	0	0	0	0%
Switch over*	-	-	-	-	-

^{*}Day one or 26 if switching over, not both.

Active Participants > = 15kg in mg per day

Day	Morning mg	Noon mg	Evening mg	Total mg/kg per day	Total mg/day	% Change
1*	0	0	75	5	75	0
2	0	75	75	10	150	100%
3	75	75	75	15	225	50%
4	75	75	75	15	225	0%
5	100	100	100	20	300	33%

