Should a clinically significant AE occur, the Study Medical Monitor will be notified. The monitor will require unblinding by the study pharmacist. The Investigator will be advised by the Medical Monitor and review with the parent/caregiver. Modifications may need to be made in the study sequence, for example, extending the time between dose increases. Any modifications in the protocol will be reflected on both the gabapentin and placebo arms.

Any AE that occurs between the time that a study participant is enrolled and the time that s/he departs the study at the end of the final study visit (or at the time of early discontinuation of the participant from the study for any reason) will be captured and recorded. At each contact with the participant, the investigator (or designate) must seek information on AEs by specific questioning and, as appropriate, by examination.

AEs that have been reported by the study participant will be followed-up for duration, intensity and possible recurrence.

All AEs (including SAEs) will be followed until resolution or until the investigator and the Medical Monitor agree that the AE has resolved, stabilized or become chronic and no further follow-up is required.

In the case of a Suspected Unexpected Serious Adverse Reactions (SUSARs) the Sponsor will expedite the reporting of the event to investigator(s), institutions(s), ethics board(s), and Health Canada per published guidelines. If the adverse reaction is not documented in the Product Monographs (new occurrence) and is thought to be related to the study treatment, the study sponsor may urgently require further information from the investigator for regulatory reporting.

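### For a child who leaves early, recording of new adverse events ends at study discontinuation, and no later contact is required to collect new non-serious events

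*Protocol*

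**What the plan says.** **Withdrawal (section 3.8, Withdrawal from trial).** The listed grounds include "Severe Adverse Events (SAE) and/or other safety reasons". On the study drug the text says: "While the treatment with the investigational product will discontinue if a participant withdraws from the trial". The second half of that sentence makes a request about assessment: "participants not completing the entire study should be fully evaluated (i.e., last study contact and follow up procedures performed), wherever possible".

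**Early termination (section 3.8, Early termination visit).** At discontinuation, staff should try to ensure three things: "Procedures and evaluations scheduled for the End of Study are performed, including the assessment of AEs"; the study drug is returned and counted; and "Study staff make an appointment for a safety follow-up visit if required". No trigger or timing is given for that visit.

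**Recording window (section 3.12, Reporting).** For a completer, any AE is recorded from enrolment until the last visit is over. For an early leaver the rule reads: "or at the time of early discontinuation of the participant from the study for any reason) will be captured and recorded". AEs already recorded are followed until they resolve, stabilise or become chronic.

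**Serious events.** Section 3.8 (Follow up) gives any child with an SAE an extra safety visit within 7 days after the final study visit, to review that event. Section 3.12 monitors SAEs over a 108-day study period.

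**Coming off gabapentin (section 3.3).** For a child already taking gabapentin at enrolment, "the subject will be weaned off of gabapentin, in a stepwise manner with 25% reductions in dose every 3rd day". The dosing tables reduce the dose in steps at the end of each active period; one row for children under 15 kg reads "21 6.7 6.7 6.7 20 -50" (per cent). The withdrawal text mentions no steps.

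**The concern.** Safety is a named reason for withdrawal, so early leavers are likely to include children who were harmed. If recording stops when they leave, an event that begins afterwards may never reach the AE log. Evaluating safety and tolerability is a secondary objective (section 2.2). Secondary outcome 5 (section 3.4) asks whether AEs on treatment stay within the frequency in the Product Monograph. Under-counting pushes that comparison towards the hoped-for answer. Section 3.12 keeps all data in the safety analysis, so an early leaver stays in the denominator while the observation time is cut short.

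**Working it through.** **Inputs.** Last active dose on day 23 in both weight groups, with zero on days 24 and 25 (dosing tables, section 3.3). Study End on day 26 of Period 2, the last column of Table 3 with an Adverse Events Log entry; I take this as the final study visit of section 3.12. Ten children (section 3.6), with withdrawn children replaced until 10 complete (section 3.8). The protocol gives no withdrawal rate.

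**Step 1. What could collect a new non-serious AE after an early leaver departs?**

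| Provision | When | Covers a new non-serious AE after departure? |
|---|---|---|
| End of Study procedures with AE assessment (3.8) | At discontinuation | No: this is when the window closes |
| Follow-up procedures (3.8) | Where possible | Not required; the Follow Up column of Table 3 holds only the Participation Questionnaire |
| Safety follow-up visit (3.8) | Optional, no timing | Not required |
| Follow-up of recorded AEs (3.12) | Until settled | No: existing events only |
| Extra visit after an SAE (3.8) | Within 7 days after the final visit | No: children with an SAE only, to review that event |
| SAE monitoring (3.12) | 108 days | No: serious events only |

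No row requires collection.

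**Step 2. AE capture after the last active dose.**
- Completer, gabapentin second: 26 − 23 = 3 days.
- Completer, gabapentin first: if day 26 is day 1 of Period 2, 3 + 25 = 28 days. If the three washout days in section 6.2 follow the 25-day period, Period 2 starts on day 29, giving (29 − 23) + 25 = 31 days.
- Early leaver: date of study discontinuation minus date of last dose. Section 3.8 records both dates, but nothing fixes the gap. It is 0 if they coincide and longer if the child stops drug and stays for the Final Study Visit.

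**Step 3. The SAE period.** Section 6.2 puts participation at about 55 days, consistent with 25 + 3 + 25 = 53. The 108 days in section 3.12 is 108 − 53 = 55 days longer, so even the window for serious events is unclear.

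**Step 4. Size.** AE frequency = children with the event / children exposed. One missed child among 10 is 1/10 = 10 percentage points; with one early leaver added to 10 completers it is 1/11 = 9.1. The chance of at least one withdrawal among 10, at an assumed rate p, is 1 − (1 − p)^10:

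| Assumed p | 5% | 10% | 20% | 30% |
|---|---|---|---|---|
| Chance of at least one | 0.401 | 0.651 | 0.893 | 0.972 |

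**Step 5. Routes off the drug.** The tables agree with their own percentages. Under 15 kg: 60, 40, 20, 10, 5, 0 mg/kg/day (−33, −50, −50, −50, −100%). At 15 kg and over: 675, 450, 300, 150, 75, 0 mg/day (−33, −33, −50, −50, −100%). Each has five downward steps ending on day 24. Section 3.8 states none for withdrawal.

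**The case against.** The protocol does not abandon early leavers. It asks for a complete evaluation, an AE assessment at discontinuation and follow-up procedures where possible. A child with an SAE gets prompt contact, a physician's evaluation and a further visit, which is more follow-up than other children receive. Section 3.12 also tells the investigator to ask about AEs at every contact, so any later contact could bring an event to light. This stands, and it limits the gap to new, non-serious events after departure. It does not close the gap: no later contact is required, and the recording rule has already ended.

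Three stronger readings are tempting and are not supported.
- **Zero days of capture after the last dose.** The cut-off is leaving the study, not the last dose, so the interval is unspecified.
- **An instruction to stop abruptly.** Return of the drug at discontinuation makes that a natural reading, but the text does not say how the drug is stopped. Nor do these documents describe any effect of abrupt stopping.
- **Every other route off gabapentin is stepwise and watched.** Section 3.8 also covers children who simply stop study medication, again with no steps stated. Table 4 has one NCCPC-R, on day 22, between day 19 and switch-over, and the wean before randomization has no assessment schedule.

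**Conclusion.** The point holds in a limited form. Section 3.12 sets a rule that ends recording of new AEs when a child leaves early, and nothing else requires collection of a non-serious event that starts later. A completer has at least 3 days of capture after the last active dose; an early leaver has no guaranteed minimum. Each affected child is worth about 9 to 10 percentage points on an AE frequency. How many would be affected cannot be said: that depends on the withdrawal rate, on whether the child was taking gabapentin rather than placebo, and on whether an event follows. The direction is known, since missed events make gabapentin look safer against the Product Monograph. A reader might infer that all harms in children withdrawn for safety are lost; the AE assessment at discontinuation and the follow-up of recorded and serious events rule that out. The manner of stopping drug at withdrawal is an unreconciled silence, not a proven contradiction.

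**What to change.** 1. In section 3.12 (Reporting), replace the early-discontinuation cut-off with recording of all new AEs through a fixed period after the last dose of study drug, at least the 3 days that a completer has.
2. In section 3.8, replace the optional safety visit with one scheduled telephone contact at the end of that period for every early leaver, including those who stop medication.
3. Align the SAE visit in section 3.8, the SAE period in section 3.12, the participation time in section 6.2 and the Follow Up column of Table 3 with this window, and state which of 108 and about 55 days applies.
4. Separately, the sponsor must reconcile the withdrawal text in section 3.8 with the stepwise reductions in section 3.3, so that it is clear how a withdrawn child comes off the product. No stopping rule is proposed here.

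The cost is one telephone call per early leaver and a short amendment. The efficacy analysis is not affected.
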